3.2. Subject Exclusion Criteria

A subject who meets any of the following criteria will be excluded from the study:

1. Prior receipt of selective FGFR inhibitor.
2. Treatment with other investigational study drug for any indication for any reason, or receipt of anticancer medications within 28 days before first dose of study drug. Subjects must have recovered (Grade ≤ 1 or at pretreatment baseline) from AEs from previously administered therapies.
3. Untreated brain or central nervous system (CNS) metastases or brain/CNS metastases that have progressed (eg, evidence of new or enlarging brain metastasis or new neurological symptoms attributable to brain/CNS metastases). Subjects with previously treated and clinically stable brain/CNS metastases and who are off all corticosteroids for ≥ 4 weeks are eligible.
4. Have a known additional malignancy that is progressing or requires active treatment. Exceptions include basal cell carcinoma of the skin, squamous cell carcinoma of the skin, carcinoma *in situ* of the cervix, or other noninvasive or indolent malignancy that has undergone potentially curative therapy.
5. Are pregnant or lactating.
6. Have abnormal laboratory parameters:
 - a. Total bilirubin $\geq 1.5 \times$ upper limit of normal (ULN; $\geq 2.5 \times$ ULN if Gilbert syndrome or disease involving liver).
 - b. AST and ALT $> 2.5 \times$ ULN (AST and ALT $> 5 \times$ ULN in the presence of liver metastases).
 - c. Creatinine clearance ≤ 30 mL/min based on Cockcroft-Gault.
 - d. Serum phosphate $>$ institutional ULN.
 - e. Serum calcium outside of the institutional normal range or serum albumin-correct calcium outside of the institutional normal range when serum albumin is outside of the institutional normal range.
 - f. Potassium levels $<$ institutional lower limit of normal; supplementation can be used to correct potassium level during the screening.
7. Known history of human immunodeficiency virus (HIV) infection or positivity on immunoassay confirmed per local standards (NOTE: HIV screening test is optional for US subjects, but subjects with known history of HIV infection will be excluded).
8. Evidence of active hepatitis B virus (HBV) or hepatitis C virus (HCV) infection.
9. Has a history or presence of an abnormal ECG that in the investigator's opinion is clinically meaningful. Subjects with a screening QTcF interval > 450 milliseconds are excluded.

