5.4.4. Criteria for Permanent Discontinuation of Study Drug

The occurrence of unacceptable toxicity not caused by the underlying malignancy will be presumed to be related to study drug treatment and will require that the study drug be permanently discontinued. Unacceptable toxicity is defined as follows:

- Occurrence of an AE that is related to treatment with the study drug that, in the judgment of the investigator or the sponsor's medical monitor, compromises the subject's ability to continue study-specific procedures or is considered to not be in the subject's best interest.
- An AE requiring more than 2 dose reductions.
- Persistent AE requiring a delay of therapy for more than 21 days unless a greater delay has been approved by the sponsor.
- Increase in QT/QTcF to > 500 milliseconds or to > 60 milliseconds over baseline. In case of a QTc > 500 milliseconds, the subject must be hospitalized and a continuous ECG monitoring must be set up until the measure of the QTc interval decreases below 500 milliseconds and until acceptable in the opinion of a local cardiologist.

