8.4. Vital Signs

Values at each scheduled visit, change, and percent change from baseline for vital signs, including systolic blood pressure, diastolic blood pressure, pulse, respiratory rate, weight, and body temperature, will be summarized descriptively.

Criteria for clinically notable vital sign abnormalities are defined in [Table 5](#). The abnormal values for subjects exhibiting clinically notable vital sign abnormalities will be listed. Alert vital signs are defined as an absolute value outside of the defined range and percentage change from baseline greater than 25%. The abnormal values for subjects exhibiting alert vital sign abnormalities will also be listed.

Table 5: Criteria for Clinically Notable Vital Sign Abnormalities

Parameter	High Threshold	Low Threshold
Systolic blood pressure	> 155 mmHg	< 85 mmHg
Diastolic blood pressure	> 100 mmHg	< 40 mmHg
Pulse	> 100 bpm	< 45 bpm
Temperature	> 38°C	< 35.5°C
Respiratory rate	> 24 breaths/min	< 8 breaths/min

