8.5. Electrocardiograms

Twelve-lead ECGs including PR, QRS, QT, and QTcF intervals, as well as heart rate, will be obtained for each subject during the study. Values at each scheduled visit, change, and percent change from baseline will be summarized for each ECG parameter. Change and percent change from baseline will be calculated using the average of all nonmissing values before the first dose of INCB054828 as the baseline value.

Criteria for clinically notable ECG abnormalities are defined in [Table 6](#). The abnormal values for subjects exhibiting clinically notable ECG abnormalities will be listed with study visit. Alert ECG values are defined as both the absolute value outside the defined range and the percentage change greater than 25% (QRS 30%). The abnormal values for subjects exhibiting alert ECG abnormalities will be identified and listed.

Table 6: Criteria for Clinically Notable Electrocardiogram Abnormalities

Parameter	High Threshold	Low Threshold
QTcF	> 460 ms	< 295 ms
PR	> 220 ms	< 75 ms
QRS	> 120 ms	< 50 ms
QT	> 500 ms	< 300 ms

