3.3.8	Shift Summary of Coagulation Values in CTC Grade – To the Worst Abnormal Value	Safety
3.3.9	Summary of Treatment-Emergent Worsening of Laboratory Abnormalities – Coagulation	Safety
3.3.10	Summary of Laboratory Values – Urinalysis	Safety
Vital Signs		
3.4.1	Summary of Systolic Blood Pressure	Safety
3.4.2	Summary of Diastolic Blood Pressure	Safety
3.4.3	Summary of Pulse	Safety
3.4.4	Summary of Body Temperature	Safety
3.4.5	Summary of Respiratory Rate	Safety
3.4.6	Summary of Body Weight	Safety
ECG		
3.5.1	Summary of PR Interval (ms) From 12-Lead ECG	Safety
3.5.2	Summary of QRS Interval (ms) From 12-Lead ECG	Safety
3.5.3	Summary of QT Interval (ms) From 12-Lead ECG	Safety
3.5.4	Summary of QTcF Interval (ms) From 12-Lead ECG	Safety
3.5.5	Summary of Heart Rate (bpm) From 12-Lead ECG	Safety
3.5.6	Summary of Outliers of QT and QTcF Interval Values From 12-Lead ECG	Safety
3.5.7	Summary of Clinically Significant ECG Abnormalities	Safety

Figures

Figure No.	Title
4.1	Forest Plot of Objective Response Rate (Efficacy)
4.2.1	Kaplan-Meier Estimates of Progression-Free Survival (Efficacy)
4.2.2	Kaplan-Meier Estimates of Duration of Response (Efficacy)
4.2.3	Kaplan-Meier Estimates of Overall Survival (Efficacy)
4.3.1	Waterfall Plot of Best Percent Change of Target Lesion Size From Baseline (Efficacy)
4.3.2	Swimmer Plot of Duration of Treatment (Efficacy)
4.3.3	Forest Plot of Progression-Free Survival (Efficacy)
4.3.4	Forest Plot of Duration of Response (Efficacy)
4.5	Kaplan-Meier Estimates of Time to Adverse Event (Safety)
4.6	Line Graph of Mean Change From Baseline for Selected Laboratory Values (Safety)

Listings

Listing No.	Title
2.1.1	Analysis Population
2.1.2	Subject Enrollment and Disposition Status
2.1.3	Subject Inclusion and Exclusion Criteria Violations
2.2.1	Protocol Deviations
2.4.1	Demographic and Baseline Characteristics
2.4.2	Oncology Disease History
2.4.3	Prior Systemic Therapy
2.4.4	Prior Surgery or Surgical Procedure
2.4.5	Prior Radiation Treatment
2.4.6	Post Therapy
2.4.7	Medical History
2.4.8	Hepatitis History
2.4.9	Prior and Concomitant Medication
2.4.10	FGF/FGFR Alterations
2.5	Study Drug Compliance
2.6.1	Best Overall Response, Duration of Response, Progression-Free Survival, and Overall Survival
2.6.2	Investigator-Reported Assessment by RECIST v1.1
2.6.3	Response Assessment: Target Lesions
2.6.4	Response Assessment: Non-target Lesions
2.6.5	Response Assessment: New Lesions

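### SAP 8.5 defines no QTcF output on the protocol's own 5.4.4 values, so some rises above 60 ms reach neither ECG listing; its notable QTcF limit (460 ms) also differs, undeclared, from the protocol's (450 msec)

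*SAP*

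**What the plan says.** SAP 8.5 plans two ECG listings.

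- **Notable values.** Any reading outside Table 6 qualifies, with no condition on change: "The abnormal values for subjects exhibiting clinically notable ECG abnormalities will be listed with study visit". For QTcF the upper limit in Table 6 is 460 ms.
- **Alert values.** Two conditions must both hold: the reading is outside Table 6, and it shows a "percentage change greater than 25% (QRS 30"%). Change is measured "using the average of all nonmissing values before the first dose of INCB054828 as the baseline value".

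SAP Appendix A also plans Table 3.5.6, "Summary of Outliers of QT and QTcF Interval Values From 12-Lead ECG". It is given by title only, and no SAP text sets its categories.

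The protocol differs in three places.

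- Section 5.4.4 names a QT criterion among its reasons for permanent discontinuation: "Increase in QT/QTcF to > 500 milliseconds or to > 60 milliseconds over baseline".
- Section 9.4.2.4, Table 10, puts the upper notable limit for QTcF at 450 msec. The other seven limits in that table agree with SAP Table 6.
- Section 9.4.2.4 has no ECG alert rule. The protocol's 25% rule is in 9.4.2.3 and covers vital signs only.

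On eligibility, protocol 3.2 states: "Subjects with a screening QTcF interval > 450 milliseconds are excluded". SAP 10.1, which should record changes to protocol-defined analyses, is marked not applicable.

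**The concern.** A 25% change is a very large movement for QTcF. The protocol treats a rise of more than 60 ms, or a value above 500 ms, as important enough to end treatment, yet nothing in SAP 8.5 is defined on those values. The only 500 ms limit in Table 6 is for uncorrected QT. A listing labelled alert could therefore be empty while some subjects had met the 5.4.4 criterion, and a subset of those subjects would not be in the notable listing either.

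The higher notable limit adds to this. Values above 450 and up to 460 ms belong in the listing that the protocol describes but not in the one the SAP will produce, and no explanation is recorded.

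**Working it through.** The plan gives no figure to reproduce here; the check compares thresholds.

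**Inputs.** Let B be the baseline QTcF and Q an on-treatment QTcF, both in ms.

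- Protocol 5.4.4 is met when Q > 500 or Q − B > 60, that is, when Q > min(500, B + 60).
- A SAP alert (high side) needs Q > 460 and Q > 1.25 × B.
- A SAP notable value (high side) needs Q > 460. Under protocol Table 10 it needs Q > 450.
- Screening QTcF may not exceed 450. The SAP baseline averages all pre-dose values, so 450 is an approximate ceiling for B.

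**Step 1: alert rule against 5.4.4.**

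| B | 5.4.4 met above | Alert above | 60 ms as % of B |
|---|---|---|---|
| 380 | 440 | 475 | 15.8% |
| 390 | 450 | 487.5 | 15.4% |
| 400 | 460 | 500 | 15.0% |
| 430 | 490 | 537.5 | 14.0% |
| 450 | 500 | 562.5 | 13.3% |

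The rise needed for an alert is 0.25 × B: 100 ms at 400 and 112.5 ms at 450. A 60 ms rise is a 25% change only at B = 60 / 0.25 = 240 ms. A subject going from 430 to 530 ms (+100 ms, 100/430 = 23.3%) meets both parts of 5.4.4 and is not an alert.

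**Step 2: what the notable listing recovers.** Every Q > 500 exceeds 460, so it is listed. If B ≥ 400, a rise above 60 ms gives Q > 460, so it is listed too. The 430 to 530 ms case is visible and lacks only the alert label.

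**Step 3: what neither listing shows.** This needs B + 60 < Q ≤ 460, which is possible only if B < 400. The band is 460 − (B + 60) = 400 − B ms wide: 10 ms at B = 390 and 20 ms at B = 380. Example: 390 to 455 ms is +65 ms (65/390 = 16.7%). It meets 5.4.4, is not above 460, and so is neither notable nor an alert.

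**Step 4: does the protocol's 450 limit close the gap?** Only partly. The 390 to 455 ms case would be listed. The band shrinks to 450 − (B + 60) = 390 − B, so 380 to 445 ms (+65 ms, 65/380 = 17.1%) would still be missed. Reconciling the two tables does not replace a category defined on the 60 ms rise.

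**Step 5: the notable limits.** 460 − 450 = 10 ms. Values above 450 and up to 460 ms are notable under the protocol and not under the SAP.

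**The case against.** The strongest reply is that the alert listing is an extra. The protocol promises only the notable listing for ECGs, and that listing already shows every QTcF above 500 ms and every rise above 60 ms from 400 ms upwards. Section 5.4.4 is a treatment rule applied during the study. Under protocol 7.5.4 the investigator reads ECGs for immediate management, and nothing says the alert listing exists to find 5.4.4 cases. Adverse events leading to discontinuation (Table 3.2.16) and clinically significant ECG abnormalities (Table 3.5.7) are tabulated separately, and Table 3.5.6 may well use the 500 and 60 ms categories.

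Most of this stands, and it limits the point to reporting. It leaves the band in Step 3, because no stated definition covers it and Table 3.5.6 has only a title.

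Three stronger readings are tempting but not supported.

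- **That the alert rule misses most 5.4.4 cases.** The documents give no QTcF distribution. With assumed normal changes, the share not labelled alert was 84–100% for a change SD of 20–40 ms and 62–71% for 60 ms. With rises spread evenly from 60 to 200 ms it was only 25–38%. Nor are unlabelled values lost: for baselines of 400 to 450 ms all of them are in the notable listing.
- **That sites would fail to act on 5.4.4.** A reporting definition does not show that.
- **That the 25% rule for temperature is a SAP error of the same kind.** Protocol 9.4.2.3 sets that rule itself, and SAP 8.4 lists out-of-range temperatures without it.

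One caution on versions: the SAP is based on Protocol Amendment 6 and the protocol at hand is Amendment 7. The itemised Amendment 7 changes do not mention Table 10, so the difference probably predates it. Whether SAP 10.1 was wrong when written cannot be confirmed.

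**Conclusion.** The point holds as a minor safety-reporting gap in two parts.

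1. No stated SAP definition uses the 5.4.4 values for QTcF. Readings that meet 5.4.4 can lack the alert label. Rises above 60 ms that end at or below 460 ms, from baselines below 400 ms, appear in neither listing. The unlisted band is 400 − B ms wide.
2. The notable QTcF limits conflict by 10 ms, with no departure recorded.

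The thresholds follow from the documents alone. How many subjects fall in the band cannot be estimated from them. The first part assumes that Table 3.5.6 and the ECG listings carry no further categories; if the table shells already use 500 and 60 ms, it reduces to writing those cut-offs into the SAP. Neither part affects the efficacy analyses.

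**What to change.** These changes concern reporting only and propose no clinical rule.

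- For QT and QTcF, replace the percentage condition in the SAP 8.5 alert definition with the values already in protocol 5.4.4 (above 500 ms; more than 60 ms over baseline), and state the same categories for Table 3.5.6.
- State which baseline the 60 ms rise uses. SAP 8.5 averages the pre-dose ECGs, SAP 4.1.3 takes the last pre-dose value, and protocol 5.4.4 does not say.
- Reconcile 450 and 460 ms between protocol Table 10 and SAP Table 6. Which document moves is for the sponsor to decide.
- Record any remaining departure from the protocol in SAP 10.1.

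The cost is a few lines of SAP text and minor reprogramming of the ECG listings and one table; a few more subjects will be listed. If Table 10 is the one to change, that also needs a protocol edit.

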9. INTERIM ANALYSES

For Cohort A (FGFR2 translocation), a futility analysis will be performed when approximately 25 subjects are enrolled into the cohort and have at least 1 tumor assessment or have permanently discontinued study treatment. Cohort A can be stopped for futility if 2 or fewer responders are observed, for which there is less than a 10% probability of claiming ORR > 15% at final analysis based on a 60-subject cohort, as initially planned before Amendment 5. This rule is just a guidance and is nonbinding.

Cohorts B (other FGF/FGFR alterations) and C (United States only; negative for FGF/FGFR alterations) can be stopped if 1 or less responders are observed within the first 10 subjects enrolled into the cohort who have at least 2 cycles of data. This rule is just a guidance and is nonbinding.

10. CHANGES AND MODIFICATIONS TO THE ANALYSIS PLAN

All versions of the SAP are listed in [Table 7](#).

Table 7: Statistical Analysis Plan Versions

SAP Version	Date
Original	12 JUN 2017
Amendment 1	15 APR 2019

10.1. Changes to Protocol-Defined Analyses

Not applicable.

10.2. Changes to the Statistical Analysis Plan

The original SAP has been updated to incorporate the Protocol Amendments 5 and 6 updates. Specific changes are outlined below:

- Subgroup analyses have been added for the primary endpoint (ORR in Cohort A) and the secondary endpoint (PFS in Cohort A).
- Renal and hepatic subgroup analyses for ORR and DOR have been added.
- Average daily dose has been updated to use duration of treatment as the denominator.
- Move analysis of largest percentage reduction in sum of diameters of target lesions from secondary efficacy parameters section to other efficacy parameters section
- Time-to-response analysis has been added.
- Investigator assessed efficacy parameters have been added as other efficacy analyses.
- Summary of weight has been moved from efficacy section to vital sign section.
- Clinical notable adverse events and time to first occurrence of clinical notable adverse events have been added.

3.2.14	Summary of Treatment-Emergent Adverse Events Leading to INCB054828 Dose Reduction by MedDRA System Organ Class and Preferred Term	Safety
3.2.15	Summary of Treatment-Emergent Adverse Events Leading to INCB054828 Dose Interruption by MedDRA System Organ Class and Preferred Term	Safety
3.2.16	Summary of Treatment-Emergent Adverse Events Leading to Discontinuation of INCB054828 by MedDRA System Organ Class and Preferred Term	Safety
3.2.17	Summary of Treatment-Emergent Non-Serious Adverse Events by MedDRA System Organ Class and Preferred Term	Safety
3.2.18	Summary of Treatment-Emergent Adverse Events and Grade 3 or Higher Adverse Events by MedDRA Preferred Term in Decreasing Order of Frequency	Safety
3.2.19	Summary of Sponsor-Defined Clinically Notable Treatment-Emergent Adverse Events by Category and Preferred Term	Safety
3.2.20	Summary of Grade 3 or Higher Sponsor-Defined Clinically Notable Treatment-Emergent Adverse Events by Category and Preferred Term	Safety
3.2.21	Summary of Serious Sponsor-Defined Clinically Notable Treatment-Emergent Adverse Events by Category and Preferred Term	Safety

Table No.	Title	Population
3.2.22	Summary of Sponsor-Defined Clinically Notable Treatment-Emergent Adverse Events Leading to Dose Reduction by Category and Preferred Term	Safety
3.2.23	Summary of Sponsor-Defined Clinically Notable Treatment-Emergent Adverse Events Leading to Dose Interruption by Category and Preferred Term	Safety
3.2.24	Summary of Sponsor-Defined Clinically Notable Treatment-Emergent Adverse Events Leading to Discontinuation of Study Drug by Category and Preferred Term	Safety
3.2.25	Summary of Sponsor-Defined Clinically Notable Treatment-Emergent Adverse Events by Category and Preferred Term: Life-Table Method	Safety
3.2.26	Summary of Grade 3 or Higher Sponsor-Defined Clinically Notable Treatment-Emergent Adverse Events by Category and Preferred Term: Life-Table Method	Safety
Laboratory		
3.3.1	Summary of Laboratory Values – Hematology	Safety
3.3.2	Shift Summary of Hematology Values in CTC Grade – To the Worst Abnormal Value	Safety
3.3.3	Summary of Treatment-Emergent Worsening of Laboratory Abnormalities – Hematology	Safety
3.3.4	Summary of Laboratory Values – Chemistry	Safety
3.3.5	Shift Summary of Chemistry Values in CTC Grade – To the Worst Abnormal Value	Safety
3.3.6	Summary of Treatment-Emergent Worsening of Laboratory Abnormalities – Chemistry	Safety
3.3.7	Summary of Laboratory Values – Coagulation	Safety
3.3.8	Shift Summary of Coagulation Values in CTC Grade – To the Worst Abnormal Value	Safety
3.3.9	Summary of Treatment-Emergent Worsening of Laboratory Abnormalities – Coagulation	Safety
3.3.10	Summary of Laboratory Values – Urinalysis	Safety
Vital Signs		
3.4.1	Summary of Systolic Blood Pressure	Safety
3.4.2	Summary of Diastolic Blood Pressure	Safety
3.4.3	Summary of Pulse	Safety
3.4.4	Summary of Body Temperature	Safety
3.4.5	Summary of Respiratory Rate	Safety
3.4.6	Summary of Body Weight	Safety
ECG		
3.5.1	Summary of PR Interval (ms) From 12-Lead ECG	Safety
3.5.2	Summary of QRS Interval (ms) From 12-Lead ECG	Safety
3.5.3	Summary of QT Interval (ms) From 12-Lead ECG	Safety
3.5.4	Summary of QTcF Interval (ms) From 12-Lead ECG	Safety
3.5.5	Summary of Heart Rate (bpm) From 12-Lead ECG	Safety
3.5.6	Summary of Outliers of QT and QTcF Interval Values From 12-Lead ECG	Safety
3.5.7	Summary of Clinically Significant ECG Abnormalities	Safety

Figures

Figure No.	Title
4.1	Forest Plot of Objective Response Rate (Efficacy)
4.2.1	Kaplan-Meier Estimates of Progression-Free Survival (Efficacy)
4.2.2	Kaplan-Meier Estimates of Duration of Response (Efficacy)
4.2.3	Kaplan-Meier Estimates of Overall Survival (Efficacy)
4.3.1	Waterfall Plot of Best Percent Change of Target Lesion Size From Baseline (Efficacy)
4.3.2	Swimmer Plot of Duration of Treatment (Efficacy)
4.3.3	Forest Plot of Progression-Free Survival (Efficacy)
4.3.4	Forest Plot of Duration of Response (Efficacy)
4.5	Kaplan-Meier Estimates of Time to Adverse Event (Safety)
4.6	Line Graph of Mean Change From Baseline for Selected Laboratory Values (Safety)

Listings

Listing No.	Title
2.1.1	Analysis Population
2.1.2	Subject Enrollment and Disposition Status
2.1.3	Subject Inclusion and Exclusion Criteria Violations
2.2.1	Protocol Deviations
2.4.1	Demographic and Baseline Characteristics
2.4.2	Oncology Disease History
2.4.3	Prior Systemic Therapy
2.4.4	Prior Surgery or Surgical Procedure
2.4.5	Prior Radiation Treatment
2.4.6	Post Therapy
2.4.7	Medical History
2.4.8	Hepatitis History
2.4.9	Prior and Concomitant Medication
2.4.10	FGF/FGFR Alterations
2.5	Study Drug Compliance
2.6.1	Best Overall Response, Duration of Response, Progression-Free Survival, and Overall Survival
2.6.2	Investigator-Reported Assessment by RECIST v1.1
2.6.3	Response Assessment: Target Lesions
2.6.4	Response Assessment: Non-target Lesions
2.6.5	Response Assessment: New Lesions
